 - b) Determine the effects of physician-focused intervention on outcomes. **Hypothesis 1b:** Outcomes will be significantly improved for patients after the physician intervention, as compared to outcomes before the physician intervention.
 - c) Determine the combined effects of the two interventions on outcomes. **Hypothesis 1c:** There will be a multiplicative effect of the two interventions that yield improvements in primary and secondary outcomes over and above the independent effects of each intervention.
- 2) **Compare the effects of the interventions on outcomes for African American versus White men.** **Hypothesis 2:** The effects of the intervention will be significantly greater among African American than White men. We will also conduct exploratory analyses of the moderating effects of other variables on outcomes (e.g., decision preferences, health literacy, race-related attitudes, disease severity, trial characteristics).
- 3) **Examine the extent to which patient-physician communication mediates the relationship between the intervention and outcomes.** **Hypothesis 3:** The quality of communication will mediate the effects of the patient and physician intervention on trial offers, and, in turn, on patient understanding of trials offered and decisions to participate. Because the specific mediational variables to be tested will emerge from the analyses related to the first two hypotheses, this is an exploratory hypothesis.

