The main coordinating site, KCI/WSU, is an NCI-designated comprehensive cancer center located in Detroit, Michigan. From 2009-2011 an average of **289** new prostate cancer patients were seen each year. Of these, on average, ~60% (n=174) were African American and ~40% (n=115) were White. The second site, JHKCC, is also an NCI-designated comprehensive cancer center providing care in Baltimore, Maryland. From 2009-2011, an average of approximately **1300** new patients with prostate cancer were seen each year. Of these, on average, 15% (~200) were African American, ~82% (n=1000) were White, and ~3% were "other".

Participants and Recruitment. Research participants will include physicians and their patients with prostate cancer.

We will recruit up to **32 physicians (medical oncologists, urologists, and radiation oncologists)** who regularly treat patients with prostate cancer at one of the two research sites (WSU/KCI or Hopkins) and who can recruit patients to available trials. [name] and/or research staff will attend a clinical staff meeting to explain the study to physicians, and then meet with interested physicians individually to answer questions and obtain consent. Physicians who consent will agree to complete baseline measures, to inform their eligible patients about this study during a regularly scheduled clinic visit (or ask another member of their clinical team to do so), to allow video recording of selected patient visits, and to complete very brief questionnaires after patient visits. They will also be told they may be asked to participate in a training intervention at a later date. Based on past studies (see reference list), we expect no physician attrition.

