The first intervention is a randomized controlled trial focused on patients. This intervention is broken into two separate but identical parts, in which half of the patient sample participates before the physician intervention, and the other half participates after the physician intervention. In the first part, patients of participating physicians will be recruited and tracked until they become eligible for a trial, at which time they will be randomized into an intervention or usual care group. They will continue their participation until: they receive a trial offer, or they have four interactions with their physician without receiving an offer. Regardless of the number of interactions, this group of patients will discontinue their active participation when the physician intervention begins. Thus, these patients will participate for a maximum of 20 months. In the second part, which occurs after the physician intervention has been conducted, the remaining half of the patient sample will be recruited and tracked, and eligible patients will be randomly assigned to the two groups. Again, their participation will continue until they receive a trial offer, they have four interactions with their physician without an offer, or data collection ends. These patients will, thus, also participate for a maximum of 20 months. We will utilize a block-randomized design in which physicians are treated as blocks and patients are randomized to a group.

The second intervention is a within-subjects interrupted time series quasi-experiment focused on physicians.³⁰ Physicians will be recruited at the beginning of data collection, prior to any patient recruitment (i.e., once IRB approval has been received—approximately nine months after the formal start date of this grant award). In this within-subjects design, physicians provide pre-intervention data for 20 months, then receive the intervention and continue their participation for another 20 months (i.e., until the end of data collection). The same physicians will remain in the study throughout data collection; thus they will provide both pre intervention and post intervention data that will be used to examine the effectiveness of the physician-focused intervention.

Figure 2: Study Design and Procedures Overview

Patient Procedures, Measures, and Intervention

Patient Procedures.

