Physician Procedures. Physician participation will involve referring their patients to the study, completing baseline measures, and completing measures immediately after clinic visits with participating patients (See Appendix B, Physician Consent). Physicians will be informed that they will be approached at a later date about the physician-focused intervention, and will be asked for re-consent at that time. As noted above, the physician intervention does not occur until 20 months after they enroll in the study, and separate IRB approval will be sought before it is implemented.

Physician Measures (See Appendix K: Physician Baseline Measures.)

Physician Baseline Measures: Within a week of recruitment, physicians will provide demographic information such as age, gender, and years in practice. They will complete measures assessing their attitudes toward trials,^{23,53} decisional control preferences,⁵⁴ attitudes toward patient-physician relationships,⁵⁵ and explicit and implicit racial attitudes (using the Implicit Association Test) toward African Americans and White people.⁵⁶ The baseline measures should take <45 minutes to complete (See Appendix N, Physician Baseline Instructions).

Clinic Visits. Following each patient visit, physicians will report whether they discussed and/or offered a trial and their perceptions of the patient's personal attributes and behavior during the visit.^{47,57} If a trial was offered, we will also ask physicians about their perceptions of how well the patient understood the trial, his ability to tolerate the trial, and his likely adherence to the trial protocol. This questionnaire should take less than 5 minutes to complete. (See Appendix L, Physician Post Interaction Questionnaire)

Physician Intervention. The physician intervention is implemented via an interrupted time series, within-subject design. Physicians receive the intervention **in Phase 2, following IRB approval and re-consent.**

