The physician-focused intervention includes two components: a communication and an attitude/awareness component. The **communication component** consists of a **web-based** communication skills training module. The objective of the training module is to improve physicians' communication skills in general (e.g., patient-centeredness, shared decision making) and specific to discussing trials with patients. **Once physicians have signed the re-consent forms, they will be provided a link to a website that will allow them to participate in the training. The training includes a didactic video that provides information about the importance of recruiting a diverse population of patients to cancer clinical trials, and encourages them to reflect on communication skills that facilitate effective patient-centered communication and shared decision-making about trials. Training methods will include brief explanations and discussions and video illustrations. The web-based materials also include questions (via a Qualtrics survey) that assess physicians' attitudes and knowledge about clinical trials, prior to and following the training. The training module takes about 1.5 hours. Physicians receive Continuing Medical Education (CME) credit and \$100.00 gift card once they complete the training. The script to the didactic video and the Qualtrics survey are attached.**

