Control variables: At the patient level of the model, we will control for factors such as decisional control preferences, relevant attitudes, health literacy, number of boosters received, disease severity, co-morbidities, whether there is an available clinical trial for the patient, and if so, characteristics of the trial (e.g., difficulty, complexity). At the physician level, we will control for relevant racial and professional attitudes, and decisional control preferences. Because the physician-focused phase involves a quasi-experimental design, we will also control factors that might threaten the internal validity of the intervention, such as time since study has begun, and number of previous interactions between patients and physicians.

Hypothesis 1a. Outcomes will be significantly improved in the patient intervention group, relative to the usual care group. To test hypothesis 1a, we will fit separate MLMs to examine continuous and binary outcomes assessed during or after each visit in which a trial was discussed. The focal independent variable will be the dummy-coded variable indicating whether the patient was in the usual care or intervention group. Support for hypothesis 1a will be indicated by a significant coefficient for this independent variable (i.e. intervention/usual care).

Hypothesis 1b. Outcomes will be significantly improved for patients after the physician intervention, as compared to outcomes before the physician intervention. The focal independent variable is the dummy-coded variable indicating whether or not the patient's physician has received the physician intervention at the time of the clinic visit. Note that this variable is a within-subject variable among the physicians; however, because we theorize that the patient-physician communication quality is central to offers and acceptance of clinical trials, this variable is introduced in the model at level-1 (patients). Support for hypothesis 1b will be indicated by a significant physician-intervention coefficient (i.e., pre/post physician intervention).

Hypothesis 1c. The combined effects of the two interventions will be multiplicative, rather than simply additive. The focal independent variable is the dummy coded variable for the product interaction term in the model. We expect the physician intervention to be more effective among patients who received the patient intervention; we expect a statistically significant positive coefficient for the interaction term.

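### The Hypothesis 1b variable is coded by receipt of training, so the before/after contrast is contaminated if any physician stays in the study untrained

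*Combined protocol and SAP*

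**What the plan says.** The hypothesis reads "Outcomes will be significantly improved for patients after the physician intervention, as compared to outcomes before the physician intervention" (Specific Aims; repeated under Hypothesis 1b in Statistical Analyses). The two phases do not overlap in patients. Under Study Design Overview, for the first half of the sample, "this group of patients will discontinue their active participation when the physician intervention begins"; the second half is recruited after it.

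The variable that carries the test is a dummy for "whether or not the patient's physician has received the physician intervention at the time of the clinic visit" (Hypothesis 1b). The same paragraph adds "Note that this variable is a within-subject variable among the physicians" and labels the tested coefficient pre/post.

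Receipt is voluntary. Physicians "will be asked for re-consent at that time" (Physician Procedures), and only after signing is it that "they will be provided a link to a website that will allow them to participate in the training" (Physician Intervention). On retention, Participants and Recruitment says "we expect no physician attrition". The plan does not say how to classify post-phase patients of a physician who stays but declines or does not finish. Nor does it say which of the intervention's two parts, the web module and the per-patient reminder cards, counts as receipt.

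The model nests patients within physicians. It controls for elapsed study time and for physician racial and professional attitudes and decisional control preferences (Control variables).

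**The concern.** Receipt and phase coincide only if every physician is trained. For a physician who stays untrained, the receipt dummy is 0 in both phases, so it is no longer within-physician. That physician's post-phase patients join the reference group, and the coefficient picks up any standing difference between physicians who accept training and those who do not. If those who decline are also those whose patients less often decide to enroll, training appears to work when it does nothing. The Hypothesis 1c and Aim 2 product terms use the same variable.

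**Working it through.** The plan gives no figure for uptake or for outcomes among untrained physicians, so there is none to reproduce on this point. From Power and Sample Size Estimates I take 24 physicians × 9 patients = 216, ICC .05, and success .25 versus .35. The planned odds ratio is (.35/.65)/(.25/.75) = 1.615, which agrees with the stated 1.61. It serves here only as a yardstick.

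**Step 1: who is coded 0.** Let f be the share of physicians who stay untrained, with equal patient numbers before and after (the plan recruits half in each phase). Group 1 has relative size 1 − f. Group 0 has size 1 + f: all pre-phase patients plus the post-phase patients of untrained physicians. The misplaced share of group 0 is f/(1 + f). Pre-phase patients of trained physicians make up (1 − f)/(1 + f).

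**Step 2: crude bias with no true effect.** Let success be p_t for patients of trained physicians and p_u for patients of untrained ones, the same in both phases. Group 1 has mean p_t. Group 0 has mean [(1 − f)p_t + 2f·p_u]/(1 + f). The difference is (p_t − p_u)·2f/(1 + f). With assumed .30 and .15 and f = .25 this is .15 × .50/1.25 = .060. Under phase coding both groups have mean (1 − f)p_t + f·p_u, so the difference is 0.

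**Step 3: what the random intercept removes.** The weight on a physician's own mean is 9 × .05/(1 + 8 × .05) = .45/1.40 = .32, so most of the between-physician difference remains. Expected coefficients on the risk scale, by generalized least squares with a physician random intercept and time running over months 0–20 and 22–42:

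| Untrained of 24 | Misplaced share of group 0 | Pre-phase patients of trained physicians in group 0 | Crude bias | Random intercept | Random intercept + linear time |
|---|---|---|---|---|---|
| 0 | 0% | 100% | 0 | 0 | 0 |
| 2 | 7.7% | 84.6% | .023 | .016 | .041 |
| 4 | 14.3% | 71.4% | .043 | .031 | .064 |
| 6 | 20.0% | 60.0% | .060 | .044 | .079 |
| 8 | 25.0% | 50.0% | .075 | .056 | .089 |

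Phase coding gives 0 in every row, as does receipt coding with physician fixed effects (both without time). The time term raises the bias because, among trained physicians, training and time move together. Untrained physicians then help to separate the two, and the coefficient leans on the concurrent comparison.

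**Step 4: effect on the test.** Null trials were simulated with 24 × 9 patients, a logistic model with exchangeable within-physician correlation, and assumed success of .15 (untrained) and .28 (others). At f = .25 the overall rate is .25 × .15 + .75 × .28 = .2475, close to the plan's .25. Ranges cover several runs that differ in detail, typically 400 to 600 trials per scenario.

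- 6 untrained, receipt with time: odds ratio 1.60–1.75, rejection about 20–25%. Without time: 1.29–1.32, rejection 13.5–17%.
- 3 untrained, receipt with time: odds ratio 1.38–1.56, rejection 9.5–15.5%.
- Phase coding: odds ratio about 0.95–1.11, rejection about 4–10% depending on the run. Robust errors with 24 clusters account for part of this: one run rejected 7.6% with nobody untrained.
- 6 untrained, receipt with time, plus one noisy physician-attitude covariate (assumed): odds ratio down from 1.60 to 1.40, rejection from .20 to .13.
- 6 untrained, receipt centred within physician: odds ratio .99 without time, 1.07 with time.
- 6 untrained, standard error with time in the model: about .65 for phase coding and .45 for receipt coding.

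At 3 untrained the shift in odds ratio appears in every run, but the excess rejection does not. One run gave 10.6% for receipt and 10.2% for phase. The simulation error at 10% with 500 trials is √(.10 × .90/500) = .013.

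**The case against.** The best defence is that the paragraph shows what was meant. It calls the variable within-subject and the coefficient pre/post, and Study Design Overview has the same physicians receiving the intervention and continuing. A physician who declines might leave the post-phase, or be coded by phase anyway. Uptake may well be complete: the module is web-based, takes about 1.5 hours, and brings CME credit and a $100 gift card, and physicians hear at first consent that training may follow. The planned attitude covariates could absorb part of any difference. Phase coding is also not the only remedy, since centring receipt within physician nearly removes the bias.

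Much of this stands. A reader might infer that the plan moves such patients into the before group. No passage says so; it follows only from applying the stated definition to a case the plan does not address. Uptake is unknown, and the covariates may help.

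Two parts do not stand. The labels show intent but do not override the only operational definition given, and they conflict with it for any untrained physician. The attrition statement sits with initial recruitment and concerns staying in the study, not accepting training.

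**Conclusion.** The concern holds in a conditional form. The written coding departs from the stated contrast as soon as one physician contributes post-phase patients untrained, and the planned model does not protect against the resulting selection.

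Under the assumed rates (15% versus 28%, no true effect, no trend) and with time in the model, the spurious odds ratio is about 1.4 to 1.6 for 3 of 24 untrained and 1.6 to 1.75 for 6 of 24. The latter is about as large as the planned 1.61. Rejection is roughly 10–15% and 20–25%, with the lower pair hard to separate from small-cluster inflation. The decline rate, the outcome gap and its direction are all assumptions. The bias is smaller if attitude covariates predict declining, and nil if everyone is trained.

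Two stronger readings go too far. One is that Hypothesis 1b becomes a comparison of willing with unwilling physicians. Even with 6 of 24 untrained, 60% of the reference group is still pre-phase patients of trained physicians. The other is that the trial will have a 20–25% false-positive rate, which the documents cannot support because they give neither uptake nor a gap.

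**What to change.** For the primary test, define the Hypothesis 1b variable by study phase (pre-phase or post-phase cohort) for all enrolled physicians who contribute post-phase patients, whether or not they re-consent or complete training. Use that variable in the Hypothesis 1c and Aim 2 product terms. State what counts as receipt, and report the receipt-coded model, centred within physician, as a sensitivity analysis.

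This takes a few lines of plan text and changes nothing if all physicians are trained. Otherwise there are two costs. The estimated effect is diluted by untrained physicians. With time controlled, the standard error is also larger (about .65 versus .45 with 6 untrained), because receipt coding borrows its precision from the biased between-physician comparison.

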We will use Multi-Level Models (MLMs) that include separate variables identifying both interventions, as well as a variable indicating the interaction between the two phases. This model allows us to examine the main effect of each intervention, and multiplicative effects of having been exposed to both interventions. For purposes of clarity, we discuss hypotheses for each intervention separately, but as already noted, they will be tested in the same MLMs. We will model most outcomes (specifically, patients' perceptions of patient-centeredness, perceived involvement in care, trust in physician, and team perceptions; patient active participation, and physician patient centeredness, patient understanding of informed consent) as continuous variables. We will use binomial logistic models for binary outcomes (e.g., trial offer) and multinomial logistic regression for categorical outcomes (e.g., patients' self-reported participation decision - "yes", "no", "undecided"). We will also explore whether a single model best captures the meditational processes for both Black and White patients or separate models are needed.

Models for Aim 1: As we have described the objectives and outcomes above, here we generally describe the models that will be used to test support for our hypotheses. All outcomes, and coefficients for each of the intervention effects and interactions between them, will be modeled at the patient level of the model (level-1); that is, they will be nested within physicians (level-2). We will use one MLM for each outcome to test the three Aim 1 hypotheses. We use this particular approach to examine the interventions' effects because it is believed that the two interventions will not only work independently, but also interactively. Thus, we use a model that simultaneously controls for the main and interactive effects of both interventions as we examine their unique contributions.

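### The product term prescribed for Hypothesis 1c tests departure from additivity in the linear models but departure from multiplied odds for the trial decision, and the plan names no scale

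*Combined protocol and SAP*

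**What the plan says.** Under Models for Aim 1, Hypothesis 1c reads "The combined effects of the two interventions will be multiplicative, rather than simply additive". The same paragraph gives the test: "The focal independent variable is the dummy coded variable for the product interaction term in the model". It adds a directional expectation, that the physician intervention will work better in patients who also had the patient intervention, and closes with the decision rule: "we expect a statistically significant positive coefficient for the interaction term".

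The Specific Aims also call the effect multiplicative, and describe improvement "over and above the independent effects of each intervention". The Statistical Analyses section uses the same label for the model: "This model allows us to examine the main effect of each intervention, and multiplicative effects of having been exposed to both interventions".

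On model form the section says: "We will use binomial logistic models for binary outcomes (e.g., trial offer) and multinomial logistic regression for categorical outcomes". Most other outcomes are modelled as continuous. The patient's participation decision (yes, no or undecided) is the example given for the multinomial model, while Power and Sample Size Estimates treats the primary outcome as a binary success. Either way it is analysed on a log-odds scale. Enrolment is not listed by name but is naturally binary, so it would fall under the logistic models.

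Nowhere does the plan say whether multiplicative and additive refer to odds, risks or percentage points.

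**The concern.** The hypothesis sets a multiplicative effect against an additive one, so additivity is the benchmark to beat. A product term tests that benchmark only where the model is additive without it. This is true of the linear models for communication and perception scores. It is not true of a logistic or multinomial model, where main effects alone already multiply on the odds scale. There the null of the product term is multiplied odds, and a positive coefficient means more than multiplied odds.

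The same rule therefore answers different questions across outcomes. For the primary outcome it does not test departure from additivity. What is at stake is the reading of a null. Two interventions could jointly raise the rate of decisions to enrol by more than the sum of their separate effects and still give a product coefficient of zero. With no scale fixed beforehand, one could also be chosen after the results are seen. Hypothesis 1c is one of three Aim 1 hypotheses, and possible multiplicative effects are part of the plan's rationale for a multilevel study.

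**Working it through.** **Inputs from Power and Sample Size Estimates.** Success rates .25 and .35; b = 0.48; odds ratio 1.61; 216 patients; α = .05.

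**Assumptions.** Each intervention alone raises the rate to .35. Cells are equal, 216/4 = 54 patients (half the sample before the physician intervention; 1:1 allocation, a ratio the plan does not state). Tests are two-sided. Physician clustering and covariates are ignored.

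**1. The plan's effect size.** logit(.35) − logit(.25) = −0.619 − (−1.099) = 0.480. The odds ratio is (.35/.65)/(.25/.75) = 1.615. Both agree with the plan. It gives no power figure for the product of the two interventions.

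**2. What a zero product term implies.** The model is logit p = b0 + b1·patient + b2·physician + b3·patient·physician. With b3 = 0, the odds with both are (1/3) × 1.615² = 0.870, so p = 0.870/1.870 = .465. Additivity in percentage points gives .25 + .10 + .10 = .45. The physician intervention then adds 10 points without the patient intervention (.25 to .35) and 11.5 points with it (.35 to .465), while b3 is exactly 0.

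**3. The two tests compared.**

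- Logit product term: b3 = logit(both) − logit(patient only) − logit(physician only) + logit(neither), with SE = √Σ 1/(54·p(1−p)). In the first row below, √(0.0988 + 0.0814 + 0.0814 + 0.0744) = 0.580.
- Probability contrast: p(both) − p(patient only) − p(physician only) + p(neither), with SE = √Σ p(1−p)/54. In the first row, √(0.00347 + 0.00421 + 0.00421 + 0.00461) = 0.128.
- Chance of a significant positive result: Φ(estimate/SE − 1.96).

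| Rates: neither / patient only / physician only / both | b3 (SE) | Chance | Contrast (SE) | Chance |
|---|---|---|---|---|
| 25/35/35/46.5%, odds multiply | 0 (0.580) | .025 | 0.015 (0.128) | .033 |
| 25/35/35/45%, points add | −0.06 (0.580) | .019 | 0 (0.128) | .025 |
| 25/35/35/49%, risks multiply | +0.10 (0.579) | .037 | 0.04 (0.129) | .050 |
| 25/35/35/60%, stronger synergy | +0.54 (0.582) | .15 | 0.15 (0.128) | .22 |
| 10/25/25/50%, illustrative rates | 0 (0.691) | .025 | 0.10 (0.115) | .14 |

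A simulation of the first row (200,000 runs, no physician effects) gave .024 for the product term.

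In the last row both odds ratios are 3 and they multiply exactly. The physician effect is 15 points without the patient intervention and 25 points with it, yet the product coefficient is zero.

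**4. Scale of the power limit.** At the third row's SE, 80% power for the product term needs b3 = (1.96 + 0.84) × 0.579 = 1.62, a ratio of odds ratios of about 5.

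**The case against.** The strongest reply is that the plan defines its own term. Right after stating the hypothesis it says: "We expect the physician intervention to be more effective among patients who received the patient intervention; we expect a statistically significant positive coefficient for" the product term. On that reading multiplicative is a label for effect modification, and exact multiplication of odds ratios, with the same physician odds ratio in both patient groups, is the null. The logit product term is then a conventional, prespecified test of the intended hypothesis. This reading is permissible. It does not settle the matter, because that sentence names no scale either. On the probability scale it can be true (10 against 11.5 points) while the coefficient is zero.

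A reader might infer that the rule rejects Hypothesis 1c when it is true. The documents do not support that. A non-significant term only fails to support the hypothesis, and the exact conflict arises only if multiplicative refers to odds. If risks multiply, the coefficient is positive (+0.10), as the plan expects, though almost undetectable.

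A reader might also infer that additive effects would look like interference between the interventions. At −0.06 the coefficient is about a tenth of its standard error. A significant negative result would occur about 3.2% of the time, against 2.5% under a zero coefficient, so this worry is negligible. Nor does the plan say that a null would be reported as no combined effect; Hypotheses 1a and 1b are tested in the same model.

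It can also be said that a probability contrast would rarely change the result. At the plan's rates with multiplied odds that is right: .033 against .025. In the larger examples it is more sensitive (.22 against .15, and .14 against .025), but still weak.

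**Conclusion.** The point holds as a mismatch of scale and interpretation. For logit-scale outcomes, including the primary one, the stated rule tests departure from multiplied odds, while the hypothesis as worded names additivity as the benchmark. If odds ratios multiply exactly, Hypothesis 1c is supported on the primary outcome only at the false-positive rate, about 2.5% in the positive direction, although the combined rate (46.5%) exceeds the additive one (45%). The linear models are not affected.

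The zero coefficient under multiplied odds is algebra and does not depend on sample size. It applies to each logit contrast if the decision is modelled as multinomial. The percentages depend on the assumed .35 for each single intervention, and the standard errors on 54 patients per cell without clustering. If the sponsor does mean more than multiplicative on the odds scale, the test is right and the wording needs correcting. Either way the plan needs an edit.

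**What to change.** State the scale in Hypothesis 1c for each type of model, then:

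- Keep the logit product term for binary and categorical outcomes, labelled as a test of more-than-multiplicative odds.
- For binary outcomes, prespecify p(both) − p(patient only) − p(physician only) + p(neither) as the test of departure from additivity. For the multinomial decision, use the probability of 'yes'. Standardise it from the same fitted model, say over which covariate distribution, and give a delta-method or bootstrap interval that respects physician clustering.
- Report both scales, and state that a null logit product term does not show that effects are merely additive or that there is no combined effect.

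The cost is a few lines of plan text and one post-estimation step, with no new data. The limitation is power: with about 54 patients per cell the contrast has a standard error near 0.13, so even a 15-point excess over additivity would be detected only about 22% of the time. That should be stated beside the result.
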